Secondary Aim: Define the effects of NMES on self-reported physical function and quality of life at 4 weeks from baseline. We hypothesize that NMES will improve quality of life and self-reported physical function compared to the control.

METHODS AND PROCEDURES

Study Design: Describe the research design, including a description of any new methodology and its advantage over existing methodologies.

Study design: We will use a randomized-controlled trial design. Patients admitted for heart failure will be recruited and randomized to NMES or control for 4 weeks following hospital discharge. Patients will be stratified by sex and age. Baseline testing will occur prior to discharge and consist of functional assessment by 6MW and SPPB and completion of 2 questionnaires regarding quality of life and physical function (Kansas City Cardiomyopathy questionnaire {KCCQ} and (Medical Outcomes Study Short Form-36 {MOS SF-36}). After completion of the 4 week intervention period, patients will undergo Post-Testing which will be identical to Baseline testing.

Inclusion/Exclusion Criteria: Patients will be recruited if they: 1) have clinical diagnosis of heart failure being actively managed during hospitalization, 2) live within 30 miles of UVMMC and are between 50-90 years of age. Patients will be excluded if they have: 1) severe dementia/alzheimer's disease 2) an active malignancy, excluding non-melanoma skin cancer or low-grade prostate cancer under active surveillance; 3) exercise-limiting vascular or neuromuscular disease; 4) body mass index $\geq 40 \text{ kg/m}^2$ or 5*) an existing lower extremity blood clot or implantable cardioverter-defibrillator (ICD) or pacemaker (PPM).¹⁴ *The last criteria is a contraindication for NMES and we will withdraw patients if they develop a blood clot or receive an ICD or PPM.

Randomization and blinding: Patients will be randomized prior to hospital discharge to NMES or control using Pocock and Simon's covariate-adaptive randomization for which sex and age will be stratified. The unblinded project manager will train patients to use NMES device and oversee them during the intervention. The PI and co-I will be blinded to treatment assignment.

Interventions:

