Usual care: Patients will not receive an NMES device. We opted not to use "sham" stimulation (eg, low-intensity stimulation below the threshold to initiate contraction) lessen the chance that patients may increase stimulation to produce contractions if there is perceived benefit. Patients will be contacted weekly to assess overall recovery. As there is currently no standard of care rehabilitation for these patients following discharge and NMES does not have demonstrated benefits, our study meets the requirements for clinical equipoise.

NMES: NMES will be carried out bilaterally on the quadriceps using a portable stimulator. Two adhesive electrodes will be placed to the anterior surface of each thigh. Symmetrical, biphasic pulses (400 μ s duration at 25 Hz) will be used, with a duty cycle of 25% (10 s on, 30 s off). Patients will be trained to conduct NMES sessions and will select stimulation intensities sufficient to cause visible muscle contractions below their pain threshold. Training in the use of the NMES device will begin prior to hospital discharge. After discharge, NMES sessions will occur 5 d/wk once per day for 45 min per occasion (5 min low-intensity warm-up, 40 min higher-intensity stimulation) for 4 wks. This program is meant to mimic an aerobic-type exercise stimulus and similar to prior protocols. Daily logs and weekly phone calls will be used to monitor compliance to maximize intervention fidelity with overall compliance measured using the device software.

Outcomes: The primary outcome is 6MW. Functional capacity measures and quality of life measures will be obtained at baseline (prior to hospital discharge) and at 4 weeks.

1. Baseline characteristics including age, body mass index, length of hospital stay, medications, and smoking status
2. Functional Capacity measures:
 - a. 6-MW test is a well-validated method to assess functional capacity in patients with cardiac disease and shows convergent validity with other indices of physical function. The test will be conducted under standardized conditions, as described by us.^{11,15} Distance walked (m) will be the primary outcome.
 - b. SPPB will be measured, as it is a widely used, easy to measure index of physical function in older adults. Thus, it provides context for the severity of disability in our population and the modifying effects of NMES for comparison to other studies.¹¹
3. Quality of Life measures:

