Statistical Considerations: *Delineate the precise outcomes to be measured and analyzed. Describe how these results will be measured and statistically analyzed. Delineate methods used to estimate the required number of subjects. Describe power calculations if the study involves comparisons. Perform this analysis on each of the primary and secondary objectives, if possible.*

Statistical Analysis:

Primary outcome is the 6MW. Other outcomes include SPPB, KCCQ and MOS SF-36 questionnaire results and subsequent ER visits and hospitalizations. The two experimental groups will be compared on baseline demographic characteristics using one-way Analysis of Variance (ANOVA) for continuous measures and chi-square tests (or Fisher's Exact Test) for categorical variables. Our primary outcome is to assess changes in physical function (specifically 6MW) between study groups to test whether NMES improves functional recovery from discharge to 4 weeks. We will use analysis of covariance to model primary and secondary outcomes, as this is the preferred model to assess data in pre-post RCTs. In this model, the 4-week post-discharge value is the dependent variable and the value at hospital discharge is a covariate. Sex interactions for response to NMES will be examined. We will assess QOL by questionnaires to determine if NMES improves patient-reported QOL vs. usual care. Clinical and other factors that may modify the response to NMES (eg, length of stay, etc) can be included in the model to control for potential confounders that might differ by group in the event that randomization fails to equate groups.

Sample Size Calculation:

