The proposed sample of 60 participants is based on having sufficient power to calculate differences in our primary outcome (6MW) between the control condition and the intervention and accommodating for potential drop outs (20%) from the study.¹¹ Power is estimated to be 80% to detect a difference in the change in 6MW between the 2 groups at the $p<0.05$ level. These estimates are based on data from a meta-analysis of RCTs of NMES in *stable* patients with chronic heart failure which detected a difference of 47 m between NMES group vs placebo as well as our pilot data of CABG patients, where patients randomized to NMES increased 6-MW distance 73 m further than controls.¹¹ We assume a 6-MW distance of 250 ± 60 m (mean \pm SD) at hospital discharge in both groups. Additionally, we have reduced the improvement in 6-MW distance in the NMES group by ~30% to 50 m (6-week post-discharge NMES: 250 ± 60 m vs. Control: 300 ± 60 m) to be conservative. This magnitude improvement in 6-MW is similar to meaningful changes found in 6-MW performance in older adults with mild- to moderate mobility disability undergoing home-based strength training (47 m) and is twice the minimal clinically significant difference in patients with cardiac disease following CR (25 m).¹⁸ Therefore, we will need to recruit 60 patients with our target of 48 patients to complete the study (n=24/group), assuming a drop out of 20%. We have not performed sample size estimates for SPPB or secondary outcomes, as extrapolating the ability of NMES to affect other variables is challenging barring relevant preliminary data, particularly in *recently hospitalized* heart failure patients.

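### Patients are allocated by minimisation on sex and age, but the primary ANCOVA commits only to the discharge walk; adding both factors costs almost nothing, for a gain that is unknown and may be negligible

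*Combined protocol and SAP*

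**What the plan says.** The methods state twice how patients are allocated. Study Design: "Patients will be stratified by sex and age". Randomization and blinding specifies Pocock and Simon's method, described as "covariate-adaptive randomization for which sex and age will be stratified". Neither place says how age is banded or gives the biased-coin probability.

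Statistical Analysis sets one ANCOVA for primary and secondary outcomes: "In this model, the 4-week post-discharge value is the dependent variable and the value at hospital discharge is a covariate". It does not call this the only covariate, but it names no other fixed term. Sex appears once: "Sex interactions for response to NMES will be examined". Age is absent from the model description. Other factors, with length of stay as the example, "can be included in the model to control for potential confounders that might differ by group in the event that randomization fails to equate groups".

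**The concern.** Minimisation removes most of the between-arm difference in sex and age. If these factors predict the 4-week walk beyond the discharge walk, the treatment estimate really is less variable than under simple randomisation. An ANCOVA that omits them leaves their variation in the error term, so its model-based standard error exceeds the true one. The confidence interval is then wider than it need be and the test rejects less often than 5% under the null.

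The optional-adjustment clause does not close the gap. It is discretionary, and it is triggered by groups that differ, which is what the allocation is designed to prevent for these two factors.

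What is at stake is precision in a trial with 48 expected completers. The validity of the test is not in question.

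**Working it through.** **1. The plan's own figure.** Inputs from Sample Size Calculation: 50 m difference, SD 60 m, 80% power, p<0.05 (sidedness not stated, two-sided assumed), 24 completers per group, 20% dropout.

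- SE = 60 × √(2/24) = 17.32 m, and 50/17.32 = 2.89.
- The noncentral t gives 80.7% power at 24 per group and 78.9% at 23.
- Recruitment: 48/(1 − 0.20) = 60.

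The figure is reproduced. It takes no credit for any covariate.

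**2. What sex and age could change.** Let r be the discharge-to-4-week correlation and R² the share of the remaining variance explained by sex and age. The documents give neither, so both are assumed.

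- Residual SD as stated: 60√(1 − r²), with 48 − 3 = 45 df.
- Residual SD with sex and age: 60√(1 − r²)√(1 − R²), with 48 − 5 = 43 df.
- Example, r = 0.5 and R² = 20%: 52.0 m becomes 46.5 m.

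This formula ignores chance imbalance in the covariates among completers, so simulation was used for the operating characteristics.

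**3. Simulation.** 20,000 runs per setting; 60 patients; sex 1:1; age uniform 50–90; minimisation on sex and age (<70 or ≥70) with coin 0.8; 12 lost at random; 48 analysed. The ANCOVA on the discharge walk was fitted without and with sex and continuous age. Sex ratio, age distribution, age cut, coin and loss pattern are assumptions. Power (%) is as stated v with sex and age:

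| R² | r = 0 | r = 0.3 | r = 0.5 | r = 0.7 | Type I as stated, range over r (%) |
|---|---|---|---|---|---|
| 0 | 79.6 v 78.7 | 83.1 v 82.5 | 89.5 v 88.9 | 97.4 v 97.2 | 4.8–5.0 |
| 5% | 80.2 v 80.9 | 83.5 v 84.5 | 89.9 v 90.5 | 97.4 v 97.6 | 4.5–4.7 |
| 10% | 80.4 v 83.0 | 83.7 v 86.0 | 89.8 v 91.4 | 97.7 v 98.2 | 4.1–4.4 |
| 20% | 81.2 v 87.0 | 84.8 v 89.9 | 90.8 v 94.4 | 98.0 v 99.1 | 3.4–3.7 |
| 30% | 81.7 v 91.0 | 85.2 v 92.8 | 91.8 v 96.7 | 98.5 v 99.7 | 3.0–3.2 |

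With sex and age, type I error is 4.7–5.3% in all 20 settings. A second simulation at r = 0.5 (8,000 runs, age normal and split at its mean) agrees: at R² = 20%, type I error is 3.6% v 5.0% and power 90.3% v 94.2%.

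**4. Reported and true standard error at r = 0.5.**

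| R² | Model SE as stated (m) | Empirical SD of that estimate (m) | Model SE with sex and age (m) |
|---|---|---|---|
| 0 | 15.09 | 15.21 | 15.22 |
| 10% | 15.13 | 14.70 | 14.47 |
| 20% | 15.16 | 14.25 | 13.64 |
| 30% | 15.13 | 13.73 | 12.74 |

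The as-stated SE hardly moves while the true SD falls, which is the conservatism described above.

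**5. Break-even.** At R² = 0 and r = 0 the SE rises from 17.45 to 17.59 m. Offsetting that needs 1 − R² = (17.45/17.59)² = 0.984, so R² of about 2%. Runs at R² = 2% confirm it: 17.48 v 17.44 m. On power, break-even is about 3%. Counting only the two lost degrees of freedom would put it near 0.2%, but that ignores chance imbalance and is too favourable.

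**6. Sensitivity at r = 0.5, R² = 10% / 30% (10,000 runs each).**

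- True age effect binary, age fitted as linear: type I error 4.1/2.6% as stated, 4.9/4.7% adjusted; power 90.4 v 91.4% and 92.3 v 96.2%.
- Patients ≥70 twice as likely to be lost: type I error 4.5/2.8% as stated, 5.2/4.7% adjusted.
- NMES patients ≥70 three times as likely to be lost: bias 1.5/2.7 m as stated, −0.1/0.0 m adjusted; type I error 4.1/3.4% v 4.7/5.3%.
- Coin 0.9 and age cut 75: type I error 4.4/3.0% as stated; power 90.4 v 91.7% and 91.8 v 96.9%.

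**The case against.** The planned ANCOVA is valid and at worst conservative. It already meets its 80% target to within simulation error at r = 0, and has about 90% power at r = 0.5. The size of any gain rests on assumed values, and the largest gains need a high R² together with a low r. An r of 0 says the discharge walk tells nothing about the same walk four weeks later. Below R² of about 2–3% the change gains nothing, so even its sign is unknown. Minimisation also delivers part of the precision without adjustment: at r = 0.5 and R² = 10% the as-stated estimate has a true SD of 14.70 m, against 14.47 m for the adjusted SE. Finally, a model with a sex interaction would normally carry a sex main effect, and nothing was computed for the secondary outcomes.

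Most of this stands as a limit on size. It does not remove the point. The text does not make the interaction model primary, and age is unnamed in any model. Precision that minimisation delivers is not credited in the reported interval unless the factors are in the model. The worst loss is under 1 point of power, against a possible gain of several. Extending the model to the secondary outcomes rests on the plan's use of one ANCOVA for all of them; no size is claimed there.

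**Conclusion.** The concern holds as a near-free improvement. The allocation uses sex and age, and the primary model commits to neither.

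For r from 0 to 0.5 the gain in power is at most 1 point at R² = 5%, about 2–3 at 10%, 4–6 at 20% and 5–9 at 30%. At r = 0.7 it is about 1 point or less throughout. If sex and age add nothing to the discharge walk, the cost is 0.2–0.9 points of power and 0.11–0.14 m of SE. No passage supports any particular R² or r, and the discharge walk may already carry most of the information.

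In every setting examined, omission made the test conservative or left it near 5%. The sample of 60 and the stated 80% power are unaffected, and the primary conclusion is not threatened.

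**What to change.** State the primary model as: 4-week 6MW = treatment + discharge 6MW + sex + age, with age as one continuous linear term. Use the same form for SPPB, KCCQ and SF-36, each with its own baseline value. Keep the sex-by-treatment interaction as a separate exploratory model. Label any adjustment prompted by observed imbalance, such as length of stay, as sensitivity analysis, so that the primary covariates are fixed before data are seen.

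The cost is one sentence of analysis text and two degrees of freedom. No new data are needed: both factors must be recorded to run the minimisation, and age is already among the items listed under Outcomes ("Baseline characteristics including age, body mass index, length of hospital stay, medications, and smoking status"). The sample size does not change.

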6 MW was developed to assess cardiopulmonary fitness in patients with lung and cardiac disease

(5), but has been used widely to assess disability in older adults (6) and is the most common metric used when seeking FDA approval for interventions to improve physical function. We have experience with this measure in heart failure patients (7).

Treatment phase

NMES will be carried out bilaterally on the quadriceps using a portable stimulator (EMPI Continuum). Two adhesive electrodes will be affixed to the anterior surface of each thigh: ~1 cm distal to the inguinal crease and ~5 cm proximal to the patella, just lateral to the midline of the thigh to assure that it does not interfere with incisions for vein harvest. Symmetrical, biphasic pulses (400 μ s duration at 25 Hz) will be used, with a duty cycle of 25% (10 s on, 30 s off). Patients will be trained to conduct NMES sessions and will select stimulation intensities sufficient to cause visible muscle contractions below their pain threshold. Training in the use of the NMES device will begin prior to day of discharge. . This training will consist of one session per day of ~15 min to familiarize the volunteer with the unit and the exercise/contraction stimulus. Upon discharge, NMES sessions will occur 5 d/wk once per day for 45 min per occasion (5 min low-intensity warm-up, 40 min higher-intensity stimulation) for 4 wks. This program is meant to mimic an aerobic-type exercise stimulus (8) and has been shown in heart failure patients to have functional benefits over a similar treatment period (9, 10). We acknowledge that the NMES training load is substantial, but have modeled this program on others that have shown morphological and functional effects in heart failure patients (11). At this exploratory stage, we feel that it is essential to use a stimulus that affects muscle size and function, with future studies modifying the NMES dose to establish a threshold that elicits a training effect with the highest subject compliance rate. Daily logs and weekly phone contacts will be used to track compliance, and compliance will be covertly monitored using the device software.

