Control patients will not receive an NMES device. We chose not to utilize a control NMES intervention (eg, stimulation below threshold to elicit contraction) to mitigate the possibility that patients may increase stimulation to produce muscle contractions if there is perceived benefit. Rigorous control over the NMES stimulus is preferable to controlling for any effects of sub-threshold, cutaneous electrical stimulation. Patients will be contacted weekly to assess their recovery and discuss issues related to general health to equate the degree of interaction with study personnel to that of the NMES intervention group.

Quality of Life measures: will be assessed with the following questionnaires which will be obtained at baseline (discharge) and 1 month following discharge

- a. Self-reported physical functioning assessment using the Medical Outcomes Study Short Form-36 (MOS SF-36) survey questionnaire (0-100 scale) with 100 representing excellent physical functioning
- b. Kansas City Cardiomyopathy questionnaire

Activities of Daily Living measures:

- a. Lawton Brody ADL questionnaire
- b. Katz Index of Independence in Activities of Daily Living

References cited above:

1. Ades, P. A., Savage, P. D., Cress, M. E., Brochu, M., Lee, N. M., and Poehlman, E. T. (2003) Resistance training on physical performance in disabled older female cardiac patients. *Med Sci Sports Exerc* **35**, 1265-1270
4. Rengo, J. L., Savage, P. D., and Ades, P. A. (in press) Directly measured physical function in cardiac rehabilitation. *J Cardiopulm Rehabil Prev*
5. Guyatt, G. H., Sullivan, M. J., Thompson, P. J., Fallen, E. L., Pugsley, S. O., Taylor, D. W., and Berman, L. B. (1985) The 6-minute walk: a new measure of exercise capacity in patients with chronic heart failure. *Can Med Assoc J* **132**, 919-923

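### Length of hospital stay is treated as a baseline covariate, but it is completed after randomisation and after in-hospital NMES training begins; adjusting for it can bias the 6MW effect if allocation changes the discharge date

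*Combined protocol and SAP*

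**What the plan says.** Five places in the combined protocol and SAP bear on this.

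- **Statistical Considerations, Statistical Analysis.** The primary model is an ANCOVA of 4-week 6MW on the 6MW at hospital discharge. It may be extended: "Clinical and other factors that may modify the response to NMES (eg, length of stay, etc) can be included in the model". The stated purpose is "to control for potential confounders that might differ by group in the event that randomization fails to equate groups". Length of stay is the only optional covariate named. No threshold for imbalance is given, and the list is open-ended.
- **Outcomes, item 1.** Stay is classed with variables known at entry: "Baseline characteristics including age, body mass index, length of hospital stay, medications, and smoking status".
- **Randomization and blinding.** "Patients will be randomized prior to hospital discharge to NMES or control".
- **Interventions (NMES) and Procedures, Treatment phase.** The first says "Training in the use of the NMES device will begin prior to hospital discharge". The second says "Training in the use of the NMES device will begin prior to day of discharge" and adds: "This training will consist of one session per day of ~15 min to familiarize the volunteer with the unit and the exercise/contraction stimulus".
- **Procedures, Treatment phase, on the comparator.** "Control patients will not receive an NMES device". There is no sham.

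The documents do not limit stay to the days before randomisation. They do not say how long before discharge randomisation takes place. They also do not say whether the discharge 6MW is measured before randomisation or before the first training session.

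**The concern.** Randomisation protects the comparison of arms on anything fixed at allocation. Total stay is not fixed then. Its last part falls after allocation and, in the NMES arm only, after an added open-label inpatient procedure.

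Two consequences follow. First, an arm difference in a true baseline variable is chance imbalance, but an arm difference in total stay could be chance or could be an effect of allocation. The plan's sentence would treat both as randomisation having failed to equate the groups. Second, the remedy is to put that same variable into the 6MW model. If allocation did move the discharge date, the adjusted contrast no longer estimates the effect of allocation, and the confidence interval does not allow for the discrepancy.

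**Working it through.** **1. Order of events.** Admission, then randomisation (before discharge), then NMES-arm training (before the day of discharge), then discharge, then the 4-week test. Total stay runs from admission to discharge, so it equals days from admission to randomisation plus days from randomisation to discharge. Only the first part is a baseline quantity.

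**2. The plan's own figure.** Inputs from Sample Size Calculation: difference 50 m, SD 60 m, 80% power, 0.05 level, 20% dropout. The number of sides is not stated; two-sided reproduces the plan.

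- Normal approximation: n = 2 × (1.960 + 0.842)² × 60² / 50² = 22.6, so 23 per arm.
- Two-sample t-test: 23.6, so 24 per arm, with 80.7% power at 24.
- Recruitment: 48 / 0.80 = 60.

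The stated 24 per group and 60 recruited are confirmed. Nothing below changes them.

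**3. Size of the bias.** Let b be the slope of 4-week 6MW on stay, in metres per day, given arm and discharge 6MW. Let d be the shift in stay caused by allocation, in days (NMES minus control), and take discharge 6MW as unaffected by allocation. In the linear model:

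unadjusted effect = stay-adjusted effect + b × d

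bias = stay-adjusted effect − unadjusted effect = −b × d

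The documents give neither b nor d, so both are assumed:

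| Shift d (NMES − control) | b = −2 m/day | b = −5 m/day |
|---|---|---|
| 0 days | 0 m | 0 m |
| +0.25 day | +0.5 m | +1.25 m |
| +0.5 day | +1.0 m | +2.5 m |
| +1 day | +2 m | +5 m |
| −0.5 day | −1.0 m | −2.5 m |

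Against the planned 50 m, the 1-day row is 2/50 = 4% to 5/50 = 10%. A longer stay in the NMES arm inflates the estimate and a shorter one deflates it.

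**4. Check by simulation.** With 1,000,000 simulated patients per scenario, a true effect of 50 m and discharge 6MW in the model:

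- No shift: adjusted and unadjusted estimates agree within 0.1 m.
- 1-day shift, fitted slopes −1.36, −2.71 and −4.07 m/day: bias +1.37, +2.74 and +4.09 m.
- 0.5-day shift, similar slopes: bias +0.67, +1.38 and +2.05 m.

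These agree with −b × d. In separate small-trial simulations with no true effect and 24 per arm, using days from admission to randomisation in place of total stay kept the mean adjusted difference within 0.4 m of zero, whatever the shift.

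**5. Set against sampling error.** With an assumed residual SD of 50 m, the standard error of the arm difference is 50 × √(2/24) = 14.4 m. A bias of 2 to 5 m is therefore 2/14.4 = 0.14 to 5/14.4 = 0.35 of a standard error.

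**The case against.** The strongest reply is that several things must coincide before any harm occurs: the optional adjustment is used, stay is the variable chosen, allocation shifts stay, and stay predicts 4-week 6MW after discharge 6MW is accounted for. The ANCOVA as specified contains none of this. The in-hospital exposure is a familiarisation session of about 15 minutes a day, the treatment course follows discharge, and no section makes discharge depend on completing training. If randomisation falls close to discharge, most of the stay precedes it. All of this stands, and it limits the point to a permitted analysis rather than the planned one.

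A reader might go further and infer a bias of 10 to 30% of the planned effect. That needs a 1-day shift together with slopes of 5 to 15 m per day. The documents support neither, and the steeper slopes sit badly with the plan's SD of 60 m. Take a residual SD of 50 m, a coefficient of 0.5 on a discharge walk with SD 60 m, and pre-randomisation days following a gamma distribution with mean 5 and shape 2 to 6 (variance 25/2 = 12.5 to 25/6 = 4.2). The 4-week variance is then 50² + 30² + b² × (4.2 to 12.5). At 10 m per day the SD is about 62 to 68 m, and at 15 m per day about 66 to 79 m.

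A reader might also infer that stay is to be tested formally as a check on randomisation. The planned between-group tests cover baseline demographic characteristics, and stay is not a demographic. Its role as a sign of imbalance comes only from the Outcomes list and the wording of the optional adjustment.

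What the reply does not remove is the classification. Stay is labelled baseline, it is the only optional covariate named, and nothing in the text prevents its use.

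**Conclusion.** The point holds in a limited form. The plan lists as baseline, and permits as a covariate in the primary 6MW model, a variable completed after randomisation and after arm-specific training has begun. An arm difference in it is not necessarily chance imbalance, and adjusting for it can bias the treatment effect.

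The size rests on two quantities that the documents do not give. With no shift in stay the bias is zero. With an assumed 1-day shift and a walk 2 to 5 m shorter per day of stay, it is about 2 to 5 m, or 4 to 10% of the planned 50 m, well inside one standard error.

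The documents do not support a claim that NMES training prolongs stay, or that the planned primary analysis is invalid. The case for acting is that the correction is specific and nearly free, and that it closes an open choice in a small trial.

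**What to change.** - In Outcomes, item 1, and in Statistical Analysis, replace length of stay with days from admission to randomisation.
- In Statistical Analysis, state that any covariate added beyond the planned discharge 6MW value must be fixed before randomisation.
- Keep discharge 6MW as the main covariate, and specify that it is measured before randomisation and before the first training session. A blanket rule admitting only variables fixed at randomisation, without this step, could exclude the plan's own covariate, because its timing relative to allocation is not stated.
- Report total stay by arm descriptively, labelled as a post-randomisation variable.

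The cost is one derived variable and a wording change. The variable needs the admission and randomisation dates; the documents do not describe recording the latter, so confirm that it is captured. Fixing the order of the walk test also constrains scheduling: since training starts before the day of discharge, the walk must be done before that day too. The sample size stays at 24 per group and 60 recruited.

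### Unnamed covariates may enter the primary ANCOVA if the arms look different; the covariate set should be fixed in advance and the primary model named

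*Combined protocol and SAP*

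**What the plan says.** Under Statistical Considerations, the Statistical Analysis text specifies an analysis of covariance in which "the 4-week post-discharge value is the dependent variable and the value at hospital discharge is a covariate". That covariate is unconditional. The same paragraph then adds: "Clinical and other factors that may modify the response to NMES (eg, length of stay, etc) can be included in the model", and gives the circumstance for doing so: they "can be included in the model to control for potential confounders that might differ by group in the event that randomization fails to equate groups".

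Earlier in the paragraph, "The two experimental groups will be compared on baseline demographic characteristics using one-way Analysis of Variance (ANOVA) for continuous measures", with chi-square or Fisher tests for categorical variables. No significance level is given for these tests, and the text does not say that their results decide which factors are added.

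Under Randomization and blinding, allocation uses "Pocock and Simon's covariate-adaptive randomization for which sex and age will be stratified". Neither sex nor age is named as a covariate in the ANCOVA; only sex interactions are to be examined.

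The documents do not list the candidate factors, define when the arms count as different, say who decides or when, or say whether the model with or without the additions gives the primary result.

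**The concern.** A covariate belongs in the model because it predicts the 4-week walk. A difference between the arms at randomisation is a chance event and says nothing about that. A strong predictor that happens to be balanced would be left out, and its variance would stay in the residual. A useless variable that happens to be unbalanced would be let in.

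The wording also leaves open which analysis is primary. The clause is permissive, the list is open and the imbalance is undefined, so several primary p-values could be defended once the data are seen.

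A smaller matter is that the sentence describes the factors as ones that may modify the response to NMES, while its stated purpose is confounder control. Adding a main effect does not address effect modification.

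**Working it through.** **The plan's own figure.** The Sample Size Calculation gives a 50 m difference, SD 60 m and 24 completers per arm. "Power is estimated to be 80% to detect a difference in the change in 6MW between the 2 groups" is stated "at the $p<0.05$ level". Two-sided testing is assumed, because a one-sided test would need only 18 per arm.
- n per arm = 2 × (1.960 + 0.842)² × 60² / 50² = 2 × 7.85 × 1.44 = 22.6, so 23. The t-based version gives 23.6, so 24.
- 2 × 24 = 48 completers, and 48 / 0.80 = 60 recruited. The stated numbers reproduce, so the sample size is not at issue.

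**The fixed part of the model.** Assume a correlation of 0.5 between the discharge and 4-week walks (not in the documents). The residual SD is 60 × √(1 − 0.25) = 52.0 m and the standard error is 52.0 × √(2/24) = 15.0 m. Power at 50 m is Φ(50/15.0 − 1.96) = 0.915; simulation gives 0.897–0.908.

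**How often a trigger would fire.** Assume a p<0.05 threshold and k independent candidates (neither is in the documents). The chance of at least one is 1 − 0.95^k: 5% for k = 1, 14% for k = 3 and 23% for k = 5. Sex and age would fire less often, because allocation balances them.

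**Type I error at nominal 5%.** Simulation with 24 per arm, correlation 0.5 with the discharge walk, and five independent candidates, each with the stated correlation with outcome:

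| Rule for the added covariates | Correlation 0.15 | Correlation 0.25 |
|---|---|---|
| Added only if baseline p<0.05 | 5.0% | 3.9% |
| Better of base and triggered result | 6.3% | 5.0% |
| Best single addition, condition ignored | 8.7% | 10.5% |
| Any subset, condition ignored | 11.1% | 16.7% |

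These used 6,000 replicates at 0.15 and 8,000 at 0.25, but 2,000 for the second row. Simulation standard errors near 5% are about 0.2–0.5 points, for example √(0.05 × 0.95 / 8000) = 0.24 points, so half-point differences mean little.

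A second set used 1, 3 or 5 candidates with partial correlations of 0.2–0.7:
- p<0.05 trigger: 3.0–4.8%
- p<0.20 trigger: 1.4–4.5%
- better of base and triggered: 5.1–6.1%
- all candidates fixed in advance: 4.7–5.4%
- free subset choice at partial correlation 0.3: 6.3%, 11.2% and 18.0% for 1, 3 and 5 candidates

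**Power.** Same setup; 50 m is the plan's effect and 40 m is an assumed smaller one.

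| Candidates and effect | Discharge walk only | p<0.05 trigger | Fixed in advance | Fixed minus trigger |
|---|---|---|---|---|
| Five at 0.15, 50 m | 90% | 89% | 90% | 1 |
| Five at 0.15, 40 m | 72% | 72% | 74% | 2 |
| One at 0.25, 50 m | 89% | 89% | 92% | 3 |
| Five at 0.25, 50 m | 89% | 90% | 98% | 8 |
| Five at 0.25, 40 m | 74% | 73% | 88% | 15 |

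Five candidates at 0.25 explain 5 × 0.25² = 31% of outcome variance on top of the discharge walk, which is optimistic.

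A looser trigger with strong covariates can gain power over the discharge-walk model. With three candidates at partial correlation 0.5, p<0.20 and 35 m, it reaches 0.705 against 0.615, a gain of 9 points. The fixed model reaches 0.992 there.

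**The named candidate.** Patients are randomised before discharge (Randomization and blinding), whereas length of stay is known only at discharge. It is therefore completed after randomisation, although the Outcomes list counts it among baseline characteristics.

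**The case against.** The best defence is that the primary model is more definite than the concern suggests. The ANCOVA with the discharge walk is stated outright, the additions are optional and conditional, and nothing says that an adjusted model would replace the main result. A supplementary reading is open. This stands in part: the fault is confined to the additional factors, and the text leaves their status unsettled.

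A reader might infer three stronger claims that the documents do not support.
- That type I error is 10% or more. Those figures let the analyst add covariates whether or not the arms differ, and the plan allows additions only if they do. Keeping that condition gives about 5–6% at most under a p<0.05 or p<0.20 trigger. The higher figures need the further assumption that an undefined difference can mean anything.
- That the baseline tests are the trigger. Those tests concern demographic characteristics, while the adjustment sentence concerns clinical and other factors and mentions no test. The link, the threshold and the number of candidates are all assumed here.
- That the trigger costs 15 points of power. That needs five fairly strong independent covariates and an effect below the planned 50 m. With weak covariates the loss is 1–2 points, and at 50 m with correlation 0.5 power stays near 90% either way.

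It could also be said that differences among completers need not be chance, since 20% dropout is expected. That is a missing-data question, and the clause, which speaks of randomisation failing, does not address it.

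**Conclusion.** The concern holds in a limited form. Imbalance between randomised arms is the wrong criterion for adding covariates, and the plan does not say which model is primary.

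Applied mechanically at p<0.05, the rule is nominal to mildly conservative (about 3–5%) and adds little or no power over the discharge-walk model. Fixing the same covariates in advance was at least as powerful in every scenario with prognostic candidates. The gain was about 1–2 points with weak covariates and about 8–15 points with five at correlation 0.25.

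Discretion between base and triggered results puts the error at about 5–6%. The 11–18% for free subset choice with five candidates is an extreme case, possible only because the condition is undefined, and it implies no intent.

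All sizes rest on an assumed 0.5 baseline correlation, independent candidates, simple randomisation with equal arms, and assumed prognostic strength. The direction of the comparison does not depend on the exact values. The point should be corrected, but it does not undermine the design or the sample size.

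**What to change.** - Delete the imbalance-triggered clause.
- State the primary covariates before any outcome is seen by arm, and use them whatever the baseline table shows. A suitable set is the discharge 6MW, the randomisation factors sex and age, and any other prognostic factor measured before randomisation. Length of stay should not be treated as a baseline covariate.
- Present the baseline comparison as description only, not as a basis for choosing the model.
- Label any other adjusted model a sensitivity analysis that cannot replace the primary result.

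The cost is a few sentences of SAP text, with no change to sample size, visits or patient burden. The downsides are that the option to change the primary model later is lost and a few degrees of freedom are spent from 48 expected completers.
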